### 5.3: Post randomization exclusion from data analysis:

- Previous decision that CPR should not be initiated *i.e.* terminal illness or palliative care
- No cardiac arrest, other condition (cases where EMS did not start CPR)

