#### **Effects of the Covid19 pandemic:**

- Due to the outbreak of the Covid19 Pandemic, the ILCOR and the Swedish Resuscitation Council issued temporary guidelines for lay bystander CPR in OHCA, recommending only looking for signs of life and performing chest compressions only.(26, 27) Therefore, this study was put on hold on date: 12-03-2020.
- The initial plan was to publish the Pilot-study including years 2017 and 2018. Due to the uncertainty during the Covid19-pandemic regarding whether the trial would be able to restart a decision by the steering committee was made to postpone the pilot publication.
- During the pause due to the Covid19-pandemic an independent data monitoring committee reviewed all data up until 12-03-2020 (pre-Covid19). Their recommendation was to continue the trial without modifications, please see also "11. Interim analysis and data monitoring committee".
- When the temporary Covid-19 guidelines were removed the 1 April 2022 the main trial was relaunched, and inclusion started in August 2022.
- A decision was made to include all patients during the period pre-Covid19 in the Pilot-study and the dates of the pilot-study were changed accordingly.
- To assure follow-up all, all EMS records of all calls of suspected OHCA with no matching record in SCAR will be reviewed. Please see "8. Data Collection"

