### From the Swedish Cardiac Arrest Register the following variables will be collected:

All EMS units participating in TANGO2 report to the SCAR. For all EMS treated OHCA the following variables will be collected from the Swedish Cardiac Arrest Register:

Date of OHCA, Age, Sex, Location of OHCA, CPR prior to EMS arrival, highest medical educational level of CPR provider, first recorded rhythm, defibrillation, airway management and drug administration, Return of spontaneous circulation (ROSC) and survival to admission to hospital.

In calls where there is no matching report in SCAR, ambulance records will be reviewed; if EMS has performed CPR or the patient had been defibrillated by an AED the case will be classified as "EMS treated" and corresponding variables will be extracted from ambulance records instead.

The EMS will obtain information on what type of CPR that was provided to the patient before their arrival at the scene. This information is obtained by observing on-going CPR at their arrival and asking bystanders what type of CPR they provided. EMS crew will also ask bystanders what kind of CPR training they have according to a three-leveled division of the bystander's medical educational level (a – off-duty professional caregiver, doctor, nurse; b – CPR-trained layman (including off-duty police and fire-fighters); or c – layman with no CPR training). This information is a part of SCAR, but there will be emphasis on obtaining this specific data in the TANGO2 trial. Survival is collected for primary endpoint at day 30 from SCAR through linkage with the Swedish public population register (folkbokföringsregistret). For the secondary outcome of neurologically favorable outcome CPC is obtained through SCAR. In a subset of patients (survivors treated at specifically named hospitals), a comprehensive neurological assessment using Patient Reported Outcome Measurement (PROM) related follow-up is performed between 30-90 days. This follow-up is performed by a nurse and/or behavioral therapists blinded to the intervention allocation. This comprehensive follow up will not be possible in all sites of the TANGO2 trial.

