## 10.4 Analysis step and strategy of the whole study populations

The target study population is witnessed OHCA of medical origin where any bystander at the scene has previous CPR training. All randomized calls of suspected OHCA will be included.

Patient with previous decision that CPR should not be initiated i.e. terminal illness or palliative care and cases where EMS did not start CPR for other reasons (sure signs of death, not true OHCA) will be excluded from data analysis. The remaining patients will be analyzed in the ITT population.

Blinded call audit will be used to define type of CPR instructions provided. All randomized EMS treated OHCA receiving instructions in accordance with randomized allocation will be treated as the target study population treated per protocol (PP1).

Finally, patients who are randomized but later judged as not fulfilling all criteria for inclusion before randomization, as evaluated by call audit (not witnessed, asphyxic, bystanders with no previous CPR training), will be removed and remaining patients will be analyzed as PP2.

Thus, we perform ITT analysis, PP1 and PP2 analysis based on the following patients:

Intention to treat (ITT) analysis: We define the ITT population as all included and randomized EMS treated OHCA patients that not fulfilled any exclusion criteria's.

Per protocol 1 (PP1): We define the PP population as the subset of the ITT population where the bystanders received the allocated instructions by the dispatch operator, as defined by the call audit.

Per protocol 2 (PP2): We define the PP2 population as the subset of the PP1 population where the patients fulfilled all inclusion criteria, as defined by call audit.

Please see also Consort Diagram in section 10.5.

The reasoning behind excluding patients after randomization is two-folded:

First: Dispatchers suspecting OHCA based on initial information in a phone-call do patient inclusion and randomization. In this situation there is very limited information and dispatchers are encouraged to treat all calls where the patients are not conscious and not breathing normally as suspected OHCA

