and start CPR instructions. Therefore, patients who do not have a treatable OHCA might be included and randomized. These patients can be divided in two categories, either it's not a true OHCA (the patient never suffered an OHCA, for example fainted and thus has a pulse at EMS arrival) or the patients is already dead or had a previous decision that CPR should not be initiated. Therefore, EMS treated OHCA will serve as the best possible evaluation of treatable OHCA.

Second: The reason for including all randomized EMS treated OHCA is because at the time of randomization the dispatch operator judges the call as meeting all inclusion criteria and no exclusion criteria. If call audit or EMS record later reveal that the OHCA was not witnessed, traumatic, caused by asphyxia or bystanders without previous CPR training, the initial selection still relied on the dispatcher. Therefore, further removal of patients in the PP1 analysis might interfere with the interpretation of the study intervention in a real-life setting. A secondary analysis will be performed in all patient fulfilling all inclusion (PP2).

[figure not shown]

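### Section 10.4 drops randomised patients given no EMS CPR, including those judged dead, from ITT, PP1 and PP2, so the repeat analyses cannot reveal an imbalance between arms

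*Combined protocol and SAP*

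**What the plan says.** **The exclusion.** Section 10.4 says that "cases where EMS did not start CPR for other reasons (sure signs of death, not true OHCA) will be excluded from data analysis".

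**The analysis sets (Section 10.4).** They are nested:
- ITT: "We define the ITT population as all included and randomized EMS treated OHCA patients that not fulfilled any exclusion criteria's".
- PP1, the primary set: "We define the PP population as the subset of the ITT population where the bystanders received the allocated instructions".
- PP2: "We define the PP2 population as the subset of the PP1 population where the patients fulfilled all inclusion criteria".

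**The stated reason.** Section 10.4 explains that dispatchers work with little information, so some randomised patients will not have a treatable arrest. Either there was no arrest, or "the patients is already dead or had a previous decision that CPR should not be initiated".

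**How other sections describe the same group.** Section 5.3 lists a prior decision against CPR and "No cardiac arrest, other condition (cases where EMS did not start CPR", without naming death. Section 10.5 expects 40% of randomised cases to be excluded and describes them as not being cardiac arrests. Section 10.4 also opens by saying that every randomised suspected arrest is included.

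**Who decides, and what they know.** Section 6.3 lists data management, follow-up, hospital personnel and researchers as blinded; EMS crews are not on the list. Under Section 8 crews record which type of CPR the bystander gave: "This information is obtained by observing on-going CPR at their arrival and asking bystanders what type of CPR they provided".

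**The concern.** The allocated instruction acts from randomisation until EMS or first responders arrive (Section 6.2). Whether EMS starts CPR is settled after that. When EMS does not start because the patient is judged dead, that patient is a failure on 30-day survival, yet leaves both numerator and denominator.

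If this happened more often in one arm, that arm's survival percentage would rise. An excess in the CO-CPR arm would favour non-inferiority; an excess in the S-CPR arm would work against it. Section 10.6 repeats the primary test in ITT and PP2, but both carry the same exclusion, so agreement among the three results says nothing about this source of bias.

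The margin is 1.0 percentage point, so a modest imbalance could matter.

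**Working it through.** **1. The plan's own figures (Section 10.5).**
- Recruitment goal: 3260 / (0.8 × 0.6) = 6791.7, rounded up to 6792. This reproduces the plan.
- Per arm at 1:1: 6792 / 2 = 3396.
- Excluded after randomisation: 0.40 × 6792 = 2717.
- Remaining in ITT: 0.60 × 6792 = 4075, about 2038 per arm.

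The share of the 2717 who are dead is not given.

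**2. Is any analysis set free of the exclusion?** PP2 lies within PP1, PP1 within ITT, and ITT contains only EMS-treated arrests. The answer is no, and no separate safety set is defined.

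**3. What an imbalance would do (illustration).** Assumptions: 60% of each arm would be EMS-treated, S-CPR survival is 11%, and both arms have the same number of survivors. Survivors as a share of each randomised arm are then 0.11 × 0.60 = 0.066. Let d be the extra CO-CPR patients dropped as dead, as a share of all randomised in that arm.

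Apparent CO-CPR survival = 0.066 / (0.60 − d)

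| d | Extra deaths dropped (d × 3396) | Apparent CO-CPR survival | Spurious gain over 11% |
|---|---|---|---|
| 1% | 34 | 0.066/0.59 = 11.19% | 0.19 points |
| 2% | 68 | 0.066/0.58 = 11.38% | 0.38 points |
| 3% | 102 | 0.066/0.57 = 11.58% | 0.58 points |
| 5% | 170 | 0.066/0.55 = 12.00% | 1.00 point |

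With those deaths kept, the two arms would be equal. The percentages carry over to PP1 if the 20% not receiving the allocated instruction fall evenly.

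A true deficit works the same way. CO-CPR survival of 9.5% on the 60% denominator (a 1.5-point deficit) with d = 3% appears as 0.095 × 0.60 / 0.57 = 10.0%, a deficit of 1.0 point.

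The denominator matters. If 2% and 5% are taken as shares of the EMS-treated patients instead, the gains are 0.11/0.98 − 0.11 = 0.22 points and 0.11/0.95 − 0.11 = 0.58 points.

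**4. What balanced deaths would do if added back.** Let s be the assumed share of the 2717 exclusions who are dead, split evenly between arms. A true difference of −1.0 point among treated patients is multiplied by 4075 / (4075 + s × 2717):

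| s | Deaths added | Difference becomes |
|---|---|---|
| 10% | 272 | −0.94 |
| 25% | 679 | −0.86 |
| 50% | 1358 | −0.75 |
| 100% | 2717 | −0.60 |

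Against a fixed margin, adding balanced deaths makes non-inferiority easier to show. This limits how such an analysis can be used.

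**The case against.** The strongest reply is that the plan declares and justifies the exclusion. Section 10.4 treats these patients as not having a treatable arrest, and Section 10.5 describes the exclusions as features that could not be detected at randomisation. If signs of death were present before the call, the exclusion is unrelated to arm and favours neither. That is plausible for many cases, but the plan has no rule that ensures it. The term is undefined, and entry requires a witnessed collapse.

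Several stronger readings are tempting but not supported:

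- **That deaths after a randomised instruction never count.** Deaths in EMS-treated patients are the primary outcome events, 87% to 89% of that group at the survival rates assumed in Section 10.5. A pulseless patient on whom EMS starts CPR is kept. Where there is no register match, Section 8 also keeps one defibrillated by an AED.
- **That Section 5.3 omits this exclusion.** Its parenthesis covers every case in which EMS did not start CPR. The problem is the label, which does not mention death.
- **That harm is hidden from the monitoring committee.** Section 11 gives it unblinded summaries, a safety mandate and the right to call for analyses. It reviewed all data on 1250 patients, 696 of them in PP1. That ratio is 55.7%, against a planned 48% of randomised or 80% of ITT, so it does not show whether untreated cases were included. What can be said is that no such table is prespecified.
- **That crews know the allocation when they decide.** Section 8 has them record the CPR type given, not the allocation, and does not say that this precedes the decision.
- **That exclusions by arm and reason will go unreported.** Section 10.1 promises a CONSORT diagram. The plan's own diagram was not readable in the text available to me.

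**Conclusion.** The point holds as a gap in robustness. Randomised patients judged dead and given no EMS CPR are absent from ITT, PP1 and PP2. The decision that removes them follows the intervention and is taken by unblinded crews, and no stated analysis would test whether it differs by arm.

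The documents give no evidence that an imbalance exists. The 40% exclusion rate should not be read as a death rate, because Section 10.5 describes that group as not being arrests.

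The size is therefore conditional. Under the assumptions in the working, an excess of 68 dropped CO-CPR deaths (2% of the arm) is worth about 0.4 points, and 170 (5%) the full 1.0-point margin. Balanced exclusions would not favour either arm.

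This should be changed, but it does not invalidate the primary analysis.

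**What to change.** Keep PP1, ITT and PP2 as they are. Add to Section 10.4 and Section 11:

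1. A table of post-randomisation exclusions by arm and reason (prior decision against CPR, judged dead, not an arrest), with a row for reason not established, at each monitoring committee look and at the end of the trial.
2. An ITT-level sensitivity analysis of 30-day survival by randomised arm that keeps EMS-untreated patients judged dead as non-survivors. Report it beside the primary result as supportive evidence and not as a pass/fail condition, because balanced added deaths shrink the difference towards zero. Working by randomised arm also avoids needing audited instructions, which Section 8 provides only for EMS-treated calls.

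Reconcile the wording of Section 5.3 (no arrest or another condition), Section 10.5 (not arrests) and Section 10.4 (signs of death, and the statement that all randomised suspected arrests are included).

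**Cost.** SAP wording, one table and one analysis. Section 7.3 already provides that "all EMS records of all calls of suspected OHCA with no matching record in SCAR will be reviewed". Section 8, however, describes extracting variables only for cases classed as EMS-treated, so the reason for not starting CPR must be added to that extraction. Some untreated patients may not be identifiable.

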## 10.5 Power and sample size estimation

We estimated that 3260 patients (1630 in each group) would be needed in the primary analysis PP1 to have 80% power to show that CO-CPR is non-inferior to standard CPR. This calculation is based on the assumptions that the true survival rates after 30 days (primary outcome) in the population for standard CPR is 11% compared with 13.1% for CO-CPR, and that alpha (1 tailed) is set at 2.5%.

We defined 1.0 percentage point or less as the largest difference in survival that is clinically acceptable (i.e. the non-inferiority level which imply that a difference bigger than this would matter in practise). This difference is equivalent to an NNT of 100 (one person of 100 will die among those recommended CO-CPR, due to this recommendation). The reason for accepting this difference relies on the assumption that CO-CPR is easier to teach and perform, and therefore the treatment can be offered to more victims (please see also section 9.3).

In addition, we assumed that 20% will not receive the allocated intervention (e.g. randomized to CO-CPR but received S-CPR instructions or vice versa). We also assumed that 40% of the included patients will be excluded because of exclusion criteria's not possible to detect at the randomization (not OHCA, see section 5.3). Therefore, the recruitment goal was set to 6792 ( $3260 / (0.8 * 0.6)$ ) randomized cases of suspected out-of-hospital cardiac arrest in order to receive 3260 in the primary PP1 analysis. (Please see also Consort Flow Diagram below)

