## 10. Data analytic and statistical analysis plan (SAP)

### 10.1 General statistical analysis plan

This trial is designed to investigate whether CO-CPR is no worse than S-CPR using a non-inferiority design. It has also been designed for the possible of a superiority testing. This statistical design has been chosen appropriately judged on the presumption that CO-CPR has potential clinical benefit but also is easier to perform (and therefore would lead to a higher number of patients receiving the treatment). The largest difference in 30-day survival (primary outcome) that is considered clinically relevant is 1.0 percentage point (please see also section 9.3).

Eligibility, allocation, inclusion and exclusion will be displayed in a Consort diagram. Differences in proportions between baseline characteristics and outcome will be tested by Fisher exact test. Differences in mean or medians between the treatment groups will be tested by either Student's t-test or Mann Whitney U test depending on distribution. Normality assumptions will be assessed with Kolmogorov Smirnov – test. The estimated between group differences will be presented as proportions and 95% confidence intervals (CI), which will be calculated by the asymptotic method without continuity correction. P-values below 0,05 will be considered statistically significant. Main results will be reported as proportions.

In addition, comparisons between the treatment groups (CO-CPR vs CPR) with respect to the outcomes will be adjusted for background characteristics factors through Binary logistic regression to adjust for possible imbalances due to randomization between the treatment groups. The association between treatment and primary outcome will be presented as odds ratios and corresponding 95% CI intervals. Statisticians at Karolinska Institutet will be responsible for the statistical analysis.

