### CONSORT 2010 Flow Diagram

## **10.6 Non-Inferiority and Superiority testing**

First, the primary analysis will be performed for non-inferiority in the PP1 population. If the primary analysis rejects the null hypothesis (i.e. CO-CPR is non-inferior to CPR with respect to the primary or some secondary outcomes), the comparisons between the treatment groups will also be done for superiority using 95% two sided confidence interval.(28) Second, the same analysis (first non-inferiority and then superiority) as above will be done for the ITT and PP2 population. The non-inferiority limit 1% will be used for both primary and secondary outcomes.

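### Section 10.5: at the printed rates of 11% and 13.1%, 1630 per group gives about 78% power, not the stated 80%

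*Combined protocol and SAP*

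**What the plan says.** Section 10.5 gives the only power statement for the primary analysis: "We estimated that 3260 patients (1630 in each group) would be needed in the primary analysis PP1 to have 80% power". It bases this on an assumption about survival, namely that "the true survival rates after 30 days (primary outcome) in the population for standard CPR is 11% compared with 13.1% for CO-CPR", and it adds that "alpha (1 tailed) is set at 2.5" percent. The margin is in the next paragraph: "We defined 1.0 percentage point or less as the largest difference in survival that is clinically acceptable". Section 10.6 carries the same 1% limit into the analysis.

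Section 10.5 names no sample size formula or software routine. The nearest guide is section 10.1, which says of the confidence intervals for between-group differences: "which will be calculated by the asymptotic method without continuity correction". Section 10.8 gives 1:1 allocation. The assumed losses (20% not receiving the allocated instruction, 40% excluded after randomisation) are applied after the 3260 to reach 6792 randomised, so they do not enter the power calculation for PP1.

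**The concern.** Section 10.5 prints a value for each quantity that a non-inferiority sample size for two proportions needs, so the stated size should be reproducible. It is not: the printed values lead to a larger size at 80% power, or to lower power at 1630 per group.

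The figure of 3260 is used elsewhere. It is the base for the 6792 randomised, and section 11 repeats it as the number to which the study continues. The power also depends heavily on the assumed rates. The distance being tested is an assumed benefit of 2.1 points plus a margin of 1.0 point, so a shift of a tenth of a point in either rate moves power by two to three points. The rates therefore need to be stated as precisely as they were used.

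**Working it through.** **Inputs**

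- Control rate 0.11, compression-only rate 0.131, margin 0.010, one-sided alpha 0.025, power 80%, 1630 per group: section 10.5.
- Asymptotic interval without continuity correction: section 10.1.
- 1:1 allocation: section 10.8.

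**What reproduces.** The inflation step is right: 3260 / (0.8 × 0.6) = 6791.7, rounded up to 6792.

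**Size for 80% power at the printed rates**

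- Variance sum: 0.11 × 0.89 + 0.131 × 0.869 = 0.21174.
- Distance to the margin: 0.131 − 0.11 + 0.010 = 0.031.
- n = (1.960 + 0.842)² × 0.21174 / 0.031² = 7.849 × 0.21174 / 0.000961 = 1729.4, so 1730 per group.
- In PP1: 2 × 1730 = 3460. By the plan's own inflation: 3460 / 0.48 = 7208.3, so 7209 randomised.

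The stated 1630 per group is not reproduced.

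**Power at 1630 per group**

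- Standard error: √(0.21174 / 1630) = 0.01140.
- Power: Φ(0.031 / 0.01140 − 1.960) = Φ(0.760) = 77.6%.
- Exact binomial enumeration of the planned interval at 11% and 13.1%: 77.7%. The gap is not an artefact of the normal approximation in the power formula.

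**Other standard choices at the printed rates**

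| Choice | n per group for 80% | Power at 1630 |
|---|---|---|
| Pooled variance under the null, unpooled under the alternative | 1731 | 77.6% |
| Farrington-Manning restricted variance | 1736 | 77.5% |
| Continuity correction | 1794 | 76.0% |
| One-sided alpha of 5% | 1363 | 85.9% |

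**Less usual sizing formulas at the printed rates**

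| Choice | n per group for 80% | Power at 1630 by that formula |
|---|---|---|
| Null variance at 11% in both arms, alternative variance as printed | 1638 | 79.8% |
| Control rate shifted by the margin (10% vs 13.1%) | 1665 | 79.2% |
| Arcsine on the same shifted rates | 1662 | 79.2% |
| Control-arm variance in both arms | 1600 | 80.7% |

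Some of these come close to 1630, but none gives it exactly.

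**Rounding of the rates (unpooled formula)**

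| Control | Compression-only | n per group for 80% | Power at 1630 |
|---|---|---|---|
| 11% | 13.05% | 1784 | 76.4% |
| 11% | 13.15% | 1678 | 78.9% |
| 11.05% | 13.05% | 1847 | 74.9% |
| 10.95% | 13.15% | 1623 | 80.2% |
| 10.91% | 13.1% | 1628 | 80.05% |
| 11% | 13.2% | 1629 | 80.0% |

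With control at exactly 11%, rounding of the compression-only rate alone never reaches 80%. With both rates correct to a tenth of a point, 80% is reached only near the corner 10.95% vs 13.15%.

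Solving for the control rate that gives 80% at 1630 yields 10.87%, 10.91% and 10.96% when the compression-only rate is 13.05%, 13.1% and 13.15%. If 11% is a whole-number rounding of anything from 10.5% to 11.5%, power at 1630 runs from about 60% (11.5% vs 13.05%) to about 90% (10.5% vs 13.15%).

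**The case against.** The strongest reply is that this is display precision and not a calculation error. The control rate is printed without a decimal beside a rate with one, and 10.9% vs 13.1%, which would ordinarily be written as 11%, needs only 1617 per group and gives 80.3% at 1630. Section 10.5 also names no formula, and one unprinted variant comes within 0.5% of the stated size (1638). The gap is about 6% in sample size on a figure that rests on assumptions anyway. With recruitment already in the main phase, restating it changes nothing about how the result will be judged.

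Much of this stands. The documents cannot tell rounding, an unusual formula and an error apart, so no calculation mistake is proven, and the gap is small.

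Two points do not go away. A different sizing formula could explain where 1630 came from, but the planned interval would still have about 77.7% power if the true rates are 11% and 13.1%. And if an unrounded control rate was used, the printed one is too coarse to support the statement, because the whole-number range allows power anywhere from about 60% to about 90%. Either way the text needs a change.

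**Conclusion.** The concern holds. At the rates as printed, with a 1.0-point margin and one-sided 2.5%, 1630 per group gives 77.6% power (77.7% exact), which is 2.4 points below the stated 80%. At those rates 80% needs 1730 per group, 100 more per group and 200 more in PP1.

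This takes 11% and 13.1% as exact and uses the interval of section 10.1. The interim looks in section 11 were not modelled. If the rates used were close to 10.91% and 13.1%, or 11% and 13.2%, both 1630 and 80% are right and the printed rates are what needs correcting. The materiality is modest: a planning figure that should be fixed, with no effect on the test, the margin or the analysis populations.

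**What to change.** State in section 10.5 which rates and which formula were used.

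- If 11% and 13.1% were used as printed, say that 3260 patients in PP1 (1630 per group) give about 78% power at those rates with the 1.0-point margin and one-sided 2.5%.
- If other rates were used, print them to the precision used, together with the formula that gives 1630, and leave the 80% as it is.

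The cost is one sentence. It needs no new data, patients or analyses, and the recruitment goal of 6792 can stay; 3460 and 7209 are given here only to show the size of the gap. The one drawback is a slightly less favourable power statement if the printed rates are the ones used.
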